#### **Aim 3 Primary Endpoint:** *MRI and Retrospective E-field Modeling*

Participants will undergo MRI scanning for retrospective electric field (E-field) modeling analyses, conducted in collaboration with [name] laboratory at CCNY. This secondary outcome will provide important mechanistic insight into electric field distribution and dose-response relationships relevant to clinical outcomes.

## **5.0 Inclusion & Exclusion Criteria / Study Population**

This study seeks to recruit from a broad range of individuals to ensure generalizability, though some exclusion criteria are required to ensure participant safety. Participants will be screened. The recruited sample will be 50% female. No racial or ethnic groups will be excluded during recruitment, nor will any other individuals with diverse backgrounds. However, participants must be English-speaking, as the study consent and other assessments are presented in English. Risks of tDCS to a fetus are currently unknown. Thus, women of childbearing age will be screened for pregnancy during the screening assessment and will be provided a pregnancy test prior to stimulation to confirm they are not pregnant.

### ***Inclusion Criteria***

- Ages 18–70.
- Current MDD diagnosis (MINI v7).
- Baseline PHQ-9 > 9.
- Capacity to consent
- Fluent English.

### ***Exclusion Criteria***

- Current or past diagnosis of treatment-resistant depression, defined as failure of  $\geq 2$  adequate antidepressant trials at any point. If on an antidepressant: Must be on a stable dose for  $\geq 4$  months prior to enrollment. No medication changes (dose or agent) during the study period.
- Bipolar or psychotic disorder
- Primary anxiety disorders without concomitant major depression as defined above
- Current significant suicidal ideation or behaviors require a higher level of care.
- Diagnosis of personality disorder
- Use of neuromodulation therapies (e.g., ECT, TMS, VNS) within the past 6 months.
- History of seizures, implanted cranial/ cardiac metal, or neurosurgery.
- Frequent and or severe headache
- Must be not have any contraindication to MRI (e.g. metals, implants, etc.)
- Personal history of head trauma, concussion, or TBI
- Current alcohol or substance-use disorder (moderate-severe).
- Any non-uniformities in the skin under the electrode site, including eczema, severe rashes, hyperhidrosis, communicable skin disorders, sensitive skin (ex., eczema, severe rashes), blisters, open wounds, burns, including sunburns, cuts or irritation (e.g., due to shaving), or other skin defects or lesions, as determined by clinical personnel
- Pregnancy (urine test required for women of childbearing potential).

## **6.0 Number of Subjects**

A total of N = 20 participants will be enrolled in a structured, two-phase study evaluating safety, tolerability, feasibility, and exploratory efficacy of a novel high-dose transcranial direct current stimulation (tDCS) protocol. We will recruit and aim to enroll 20 participants for an expected 12 total completed participants.

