## **1.0 Objectives / Specific Aims**

### **Aim 1: Evaluate the Safety, Feasibility, and Tolerability of High-Dose Repeated tDCS in Adults with Major Depressive Disorder**

#### **Aim 1:**

To evaluate the safety, tolerability, and feasibility of delivering high-dose transcranial direct current stimulation (tDCS) at 6 mA, administered twice daily for five consecutive days in an outpatient brain stimulation laboratory setting. Safety will be assessed by the absence of device-related serious adverse events (SAEs) (Protections (OHRP), 2010) requiring hospitalization or emergency care, and by skin assessments at each visit. Tolerability will be operationalized using the standardized tDCS Adverse Event Questionnaire (A. Brunoni et al., 2011). We hypothesize that  $\geq 80\%$  of participants will meet the “tolerated” classification, no device-related SAEs will occur, and the independent Safety Review Committee will not recommend stopping the study after reviewing safety/tolerability data from the first three participants in the run-in cohort.

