### **Aim 2: Collect Preliminary Outcome Data on Depression Symptom Improvement and Mindfulness Following High-Dose Repeated tDCS**

This aim will explore whether high-dose, twice-daily transcranial direct current stimulation (tDCS) administered over five consecutive days leads to measurable improvements in depressive symptoms and state mindfulness. All participants (n = 20) will complete validated pre- and post-treatment clinical assessments, including the Patient Health Questionnaire-9 (PHQ-9) and the Snaith-Hamilton Pleasure Scale (SHAPS), to evaluate changes in mood and anhedonia. Additionally, participants will complete the Cognitive and Affective Mindfulness Revised (CAMS-R) before and after the intervention to assess changes in state mindfulness. Finally, we will also assess potential cognitive effects—both positive and negative—on working memory,

attention, and processing speed using the PROMIS Cognitive Function measure and the Trail Making Test. While this study is not powered to test efficacy, these exploratory data will help estimate effect sizes and inform the design of a future randomized controlled trial. We hypothesize that participants will show reductions in depressive symptoms, improvements in hedonic tone, and increases in state mindfulness following the stimulation protocol.

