### **4.0 Study Endpoints**

#### ***Aim 1 Primary Endpoint: Safety, Feasibility, and Tolerability***

The proportion of participants meeting the “tolerated” classification as defined in Aim 1, based on data from the standardized tDCS Adverse Event Questionnaire and skin integrity assessments. “Tolerated” is defined as:

1. Completion of all scheduled tDCS sessions without discontinuation due to adverse events

2. No device-related serious adverse events (SAEs) requiring hospitalization or emergency care
3. No more than one transient Severe/Extreme symptom (score 4–5 on Likert scale) lasting  $\leq 30$  minutes without intervention
4. No clinically significant skin irritation, defined as skin redness  $\geq 3$  persisting  $>24$  hours or requiring medical treatment.

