**Day 1 (dose-escalation safety assessment cohort: first 3 patients enrolled):**

- 20-minute stimulation at **2 mA** → 30-minute rest period (extendable to 60 minutes if needed)
- 20-minute stimulation at **4 mA** → 30-minute rest period (extendable to 60 minutes if needed)
- 20-minute stimulation at **6 mA**

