**Day 2 (skin integrity and safety check):**

- Visual inspection of electrode sites for erythema, burns, or other skin reactions, and completion of the tDCS Adverse Event Questionnaire
- If no **serious adverse event (SAE)** requiring emergency department evaluation or hospitalization is observed, and skin integrity is deemed acceptable by clinical evaluation by on-site MD, participants will proceed to:
  - Two 20-minute stimulation sessions at **6 mA**, separated by a 30-minute-60 to 60-minute rest period for the remaining 4 days.
  - **Main Protocol (remaining 9 participants):** Progression beyond the initial safety run-in cohort will occur only after the Safety Review Committee has reviewed the adverse event data, skin integrity assessments, and tolerability questionnaire responses from the first three participants and determined that continuation at 6 mA is acceptable.
    - Same procedure as above, including consent, neuropsychological testing, pregnancy testing (if applicable), and MRI
    - Instead of starting at 2 mA, participants will start at 2 sessions/day at 6 mA (20 min each, 30-minute interval),
    - Conducted in-lab over 5 consecutive weekdays. After each session, skin and safety checks will be completed by study staff or trained personnel.

- **Post-Treatment Assessment:**

- Conducted in-person after the last stimulation session
- Virtual follow-up at 4 weeks to assess durability. Pt's will answer the same neuropsychological questions as above.

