## **13.0 Provisions to Monitor Data & Ensure Safety**

The Principal Investigator (PI), or a designated Co-Investigator (Co-I) if the PI is unavailable, will be responsible for reporting all unanticipated problems or adverse events (AEs) promptly to the Institutional Review Board (IRB). The PI or designated study team member will be present during each stimulation session to document any AEs in real-time. Screening data collected from participants will be securely stored in REDCap. Data from participants who do not qualify for the study will be securely destroyed.

The PI or Co-I will oversee device testing and the technical use of the High-Capacity tDCS (HC-tDCS) device. Participants will remain in the lab throughout the stimulation protocol, monitored continuously by study personnel and research staff. Co-Investigators will be present for all administration sessions, and participants will be closely monitored around the clock for any adverse events and tolerability concerns.

Informed consent will be obtained by the PI or Co-I, ensuring participants are fully informed about the research procedures, time requirements, potential risks and benefits, their rights to refuse or withdraw from participation at any time without prejudice, and providing contact details for the principal investigator.

Participant confidentiality will be rigorously maintained, with access to collected data strictly limited to authorized research staff. Participants' identities in databases will be protected using

alphanumeric codes, and all data will be securely stored in locked file cabinets or on secure servers accessible only by designated members of the study team.

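### The planned participant counts (20 enrolled, all 20 assessed post-treatment, 12 completed, phases of 3 and 9) cannot all be true, so the number to be stimulated at 6 mA lies anywhere from 12 to 20

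*Protocol*

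**What the plan says.** The counts appear in three sections of the protocol.

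- Section 6.0 sets total enrolment in the two-phase study at 20, then says: "We will recruit and aim to enroll 20 participants for an expected 12 total completed participants".
- Section 10.0 describes the first phase as the "dose-escalation safety assessment cohort: first 3 patients enrolled" and the second as "Main Protocol (remaining 9 participants".
- Section 1.0, Aim 2, says: "All participants (n = 20) will complete validated pre- and post-treatment clinical assessments".

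The primary endpoint depends on these numbers. Section 4.0 defines it as the proportion of participants classed as having tolerated treatment. The first criterion is "Completion of all scheduled tDCS sessions without discontinuation due to adverse events". Section 1.0, Aim 1, hypothesises that at least 80% "of participants will meet the “tolerated” classification, no device-related SAEs will occur".

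**The concern.** The two phases should add up to the number enrolled, and they do not. The statement that everyone is assessed after treatment also sits badly with an expectation that only 12 of 20 complete.

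Section 2.0 states that this device and dose have not been tested in a clinical or depressed population. How many people are planned to receive it is therefore a basic design figure. It governs how much a result of no serious events can say about safety, and how many successes the 80% target requires.

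**Working it through.** **Inputs.** From the protocol: 20 enrolled and 12 expected completed (Section 6.0); 3 in the run-in and 9 in the main phase (Section 10.0); 20 with pre- and post-treatment assessments (Section 1.0, Aim 2); target of at least 80% (Section 1.0, Aim 1).

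**Step 1: reproduce what can be reproduced.** 3 + 9 = 12, which matches the expected completers. Enrolling 20 to obtain 12 implies non-completion of 1 - 12/20 = 40%, and 12/0.60 = 20. Section 6.0 is therefore consistent within itself. The phases do not reproduce the enrolment figure: 20 - 3 = 17, not 9.

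**Step 2: look for a reading under which every statement is true.**

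- *All 20 are stimulated.* The main phase is then 17, and the 9 in Section 10.0 is wrong. The 20 in Aim 2 can stand only if completed refers to something after the Day 5 assessment, such as the four-week follow-up. The protocol does not say so.
- *Only 12 are stimulated, and 8 are lost before the first session.* The 3 and 9 can stand, but Aim 2 cannot have 20 people assessed after treatment. Some loss at this stage is possible. Section 5.0 says that women of childbearing age "will be provided a pregnancy test prior to stimulation to confirm they are not pregnant", and Section 13.0 provides that "Data from participants who do not qualify for the study will be securely destroyed". Against that, Section 8.0 has eligibility confirmed before enrolment.
- *Between 12 and 20 are stimulated, and 12 complete all sessions.* The 9 is then not the size of the main phase.

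Each reading makes at least one statement false. The number stimulated lies between 12 and 20.

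**Step 3: what the range means for safety.** With no events in n people, the exact one-sided 95% upper limit for the event rate is 1 - 0.05^(1/n).

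- n = 12: 1 - 0.05^(1/12) = 22.1%
- n = 20: 1 - 0.05^(1/20) = 13.9%

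**Step 4: what the range means for the 80% target.** The smallest count r with r/n at or above 0.80 is:

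- n = 12: 0.80 x 12 = 9.6, so r = 10, which is 83.3% (exact 95% interval 51.6% to 97.9%)
- n = 20: 0.80 x 20 = 16, so r = 16, which is 80.0% (exact 95% interval 56.3% to 94.3%)

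**Step 5: a conditional check only.** Suppose that completed means all sessions, that exactly 12 complete, and that everyone else who was stimulated counts as not tolerated, whatever the reason for stopping. With m people stimulated, the primary proportion is then at most 12/m: 100% at m = 12, 80% at m = 15 and 60% at m = 20. Under those three assumptions, 80% is reachable only if m is 15 or fewer, so at least 20 - 15 = 5 of the 8 expected losses must come before the first stimulation.

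**The case against.** The best defence is that most of the figures do reconcile. Section 6.0 explains the gap between 20 and 12, the phases add up to exactly the expected completers, and enrolment is capped at 20, so exposure is bounded. On that view, what remains is a mislabelled cohort size and an optimistic sentence in an exploratory aim. The definition of the analysis set may properly sit in a statistical analysis plan that is not shown. The Safety Review Committee's decision rests on the first three participants and is the same whether 9 or 17 follow.

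Much of this stands, and it limits how serious the point is. It does not remove the contradiction. Section 10.0 counts the run-in by enrolment and describes the 9 as the group that starts the main regimen, not as those expected to finish. An analysis plan can name a denominator, but it cannot correct conflicting counts in the protocol.

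A reader might infer two stronger criticisms, and the protocol supports neither.

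- *That the planning numbers rule out the 80% hypothesis.* The limit in Step 5 treats an expected 12 as fixed. It also counts people who stop for reasons unrelated to adverse events as not tolerated, and the wording of the first criterion leaves their status open. It does not apply if completed means the four-week follow-up.
- *That the primary proportion will be calculated among completers, so that the first criterion is met by definition.* Nothing proposes this, and Section 4.0 points the other way. Session completion would be redundant as a criterion if only people who finished every session were counted. The same section lists the proportion completing all sessions as a separate secondary endpoint, which makes sense only if non-completers are in the denominator.

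**Conclusion.** The counts in Sections 1.0 (Aim 2), 6.0 and 10.0 are wrong as written and should be corrected. That conclusion rests on addition alone. The likeliest explanation, that 3 and 9 are expected completers, is an inference that the text does not confirm.

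Until the counts are reconciled, the planned number stimulated at 6 mA is anywhere from 12 to 20. The limits in Step 3 and the success counts in Step 4 assume that the denominator is the number stimulated, and they describe the two ends of that range. No decision rule in the protocol uses those limits. The 12/m limit is a reason to check the planning numbers against the hypothesis, and does not show that they conflict.

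**What to change.** 1. State one set of numbers, split by phase, and use it in Section 1.0 (Aim 2), Section 6.0 and Section 10.0: enrolled, stimulated at least once, expected to complete all sessions, and expected to be assessed post-treatment.
2. If 3 and 9 are expected completers, label them so and give the cohort sizes separately. Replace the 20 in Aim 2 with the matching number.
3. While restating the counts, say that participants in the primary proportion means everyone stimulated at least once. Section 4.0 already suggests this reading.
4. Say what completed means in Section 6.0, and check that the expected number completing is compatible with the hypothesis of at least 80%. If it is not, change the planning numbers or the hypothesis so that they agree.

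This is rewording only, with no added participants or procedures. The cost is that the reported proportion may be less favourable than one calculated among completers.

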## **7.0 Setting**

Study activities will occur in two primary settings: the MUSC Brain Stimulation Laboratory Space and the MRI scanner at MUSC. The stimulations will take place in the Brain Stimulation Lab (5th Floor, MUSC Institute of Psychiatry), a secure outpatient neuromodulation suite equipped with adjustable treatment chairs, video monitoring, crash cart access, and on-site clinical supervision. Participants check in through the IOP outpatient research desk and are escorted to the badge-secured lab, where licensed research staff will be present.

For participants undergoing E-field modeling, MRI scans will be performed at the MUSC Center for Biomedical Imaging (CBI) located at [name], and de-identified for retrospective analysis by [name] lab at CCNY.

## **8.0 Recruitment Methods**

Recruitment for this study will be conducted through the Family Medicine Primary Care Clinics at MUSC, under the management of [name]. Primary care physicians in these clinics will identify patients with a diagnosis of depression who may be appropriate for participation. Physicians will conduct an initial screen against the study's inclusion and exclusion criteria. If a patient appears to meet preliminary eligibility requirements, and expresses interest in the study, the physician will notify the Principal Investigator and study collaborators. The research team will then follow up with the patient to confirm eligibility, provide study information, and obtain informed consent prior to enrollment.

In addition, we will also be recruiting through paper flyers and advertisements on social media such as Instagram, targeting patients in the Charleston community who may meet our inclusion and exclusion criteria. The advertisement will have information on how to reach out to a member of our team, who will then thoroughly screen them before, if applicable, consenting the participant.

## **9.0 Consent Process**

Written informed consent will be obtained either in a private room at MUSC, or in a secure location of their choosing. For patients that are unable to arrive at the lab prior to the start of the study, electronic "eConsent" will also be available. Participants will receive a copy of the consent form, either paper or electronic. Consent covers procedures, time commitment, risks/benefits, confidentiality, voluntary participation, and right to withdraw, of which the study team will describe thoroughly

In addition, participants will be prompted to ask questions throughout the consent process to further ensure understanding. Participants will be given ample time to ask questions and consider participation. After signing the consent form, they will also be offered a hard copy.

## **10.0 Study Design / Methods**

At the initial study visit, participants will undergo the informed consent process with a co-investigator. After providing written consent, participants will complete baseline

neuropsychological assessments, including the standardized tDCS Adverse Event Questionnaire, the PHQ-9, the SHAPS, and the CAMS-R. A pregnancy screening will also be conducted when applicable. Following these assessments, participants will be escorted to a room in the brain stimulation lab on the 5th floor to undergo their first tDCS stimulation session. Since MRI is being obtained for E-field modeling, and not pre vs post, the MRI can be scheduled at any point and does not have to be obtained before or during the study.

**Day 1 (dose-escalation safety assessment cohort: first 3 patients enrolled):**

- 20-minute stimulation at **2 mA** → 30-minute rest period (extendable to 60 minutes if needed)
- 20-minute stimulation at **4 mA** → 30-minute rest period (extendable to 60 minutes if needed)
- 20-minute stimulation at **6 mA**

**Day 2 (skin integrity and safety check):**

- Visual inspection of electrode sites for erythema, burns, or other skin reactions, and completion of the tDCS Adverse Event Questionnaire
- If no **serious adverse event (SAE)** requiring emergency department evaluation or hospitalization is observed, and skin integrity is deemed acceptable by clinical evaluation by on-site MD, participants will proceed to:
  - Two 20-minute stimulation sessions at **6 mA**, separated by a 30-minute-60 to 60-minute rest period for the remaining 4 days.
  - **Main Protocol (remaining 9 participants):** Progression beyond the initial safety run-in cohort will occur only after the Safety Review Committee has reviewed the adverse event data, skin integrity assessments, and tolerability questionnaire responses from the first three participants and determined that continuation at 6 mA is acceptable.
    - Same procedure as above, including consent, neuropsychological testing, pregnancy testing (if applicable), and MRI
    - Instead of starting at 2 mA, participants will start at 2 sessions/day at 6 mA (20 min each, 30-minute interval),
    - Conducted in-lab over 5 consecutive weekdays. After each session, skin and safety checks will be completed by study staff or trained personnel.

- **Post-Treatment Assessment:**

- Conducted in-person after the last stimulation session
- Virtual follow-up at 4 weeks to assess durability. Pt's will answer the same neuropsychological questions as above.

## **12.0 Data Management**

All data will be stored in the REDCap database. Information about the participant (including their identifiable private information) may have all their identifiers removed and used for future research studies or distributed to other researchers for future research without additional informed consent. After participation, REDCap data will be downloaded in Excel format to the secure MUSC server. In terms of publication, data will be published in aggregate form, so individual participants will not be identifiable in the final manuscript. No identifying information will be published.

**Confidentiality and Quality Control:** All study personnel will complete Social-Behavioral-Educational research CITI training, and also complete in-lab training regarding data security practices. Study personnel will be trained in the IRB protocol. The investigator and co-investigators will be available to monitor data collection to ensure quality, confidentiality, and adherence to the IRB protocol.

## **13.0 Provisions to Monitor Data & Ensure Safety**

The Principal Investigator (PI), or a designated Co-Investigator (Co-I) if the PI is unavailable, will be responsible for reporting all unanticipated problems or adverse events (AEs) promptly to the Institutional Review Board (IRB). The PI or designated study team member will be present during each stimulation session to document any AEs in real-time. Screening data collected from participants will be securely stored in REDCap. Data from participants who do not qualify for the study will be securely destroyed.

The PI or Co-I will oversee device testing and the technical use of the High-Capacity tDCS (HC-tDCS) device. Participants will remain in the lab throughout the stimulation protocol, monitored continuously by study personnel and research staff. Co-Investigators will be present for all administration sessions, and participants will be closely monitored around the clock for any adverse events and tolerability concerns.

Informed consent will be obtained by the PI or Co-I, ensuring participants are fully informed about the research procedures, time requirements, potential risks and benefits, their rights to refuse or withdraw from participation at any time without prejudice, and providing contact details for the principal investigator.

Participant confidentiality will be rigorously maintained, with access to collected data strictly limited to authorized research staff. Participants' identities in databases will be protected using

alphanumeric codes, and all data will be securely stored in locked file cabinets or on secure servers accessible only by designated members of the study team.

